8.6.9 Additional efficacy assessments

8.6.9.1 Lesion status

Lesion status (i.e., responses to the question “What is the status of the lesion?” in the follow-up lesion assessment eCRF page), will be summarized separately for each follow-up visit, as count and percentage in a per-lesion analysis. The number and percentage of lesions for each category will be given, together with a 95% CI based on Wilson (1927).

This analysis will also be performed separately

- For patients with <3 freeze cycles and <3 thaw cycles
- By procedure method (laparoscopic and percutaneous)
- By procedure method (laparoscopic and percutaneous) in patients with <3 freeze cycles and <3 thaw cycles
- By needle type (Needles with the cautery feature [IceRod CX, IceFORCE 2.1 CX, and IcePearl 2.1 CX] vs other types)

The following baseline results will be provided for lesions with a status of ‘No longer present’ at any follow-up visit:

- Number and percentage of lesions that are cystic or solid at baseline
- Baseline lesion size, by greatest trans-axial diameter, will be summarized with descriptive statistics and also as categories of ≤ 4 cm and > 4 cm
- Number and percentage in each frozen section pathology result category at baseline
- Number and percentage in each permanent section pathology result category at baseline

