6.4. Renal Lesion Size

There are no strict exclusion criteria with regard to lesion size. The typical renal lesion suitable for cryoablation is ≤ 4 cm, however, as TRACE is an observational study of the real-world outcomes of cryoablation surgery using Galil Medical products, physicians are to use their training and experience to determine the size of a renal lesion that is appropriate for cryoablation.

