4.4 Determination of Sample Size

Approximately 250 patients are expected to participate in TRACE. As the registry is an observational, non-comparative study, power calculations have not been performed. The estimated sample size has been established to help ensure an adequate population of “completed patients,” defined as those patients completing four or more years of follow-up, at the closure of the registry. This study is not powered for formal statistical analysis.

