history of both hypertension and diabetes; and by NS categories at baseline of low, moderate and high complexity (as defined in Section 6.3).

- Blood urea nitrogen (BUN)
- White blood cell (WBC)
- Hematocrit
- Hemoglobin
- Platelets
- Alanine aminotransferase (ALT)
- Aspartate aminotransferase (AST)
- Alkaline phosphatase (serum) (ALP)
- Alkaline phosphatase (plasma) (AKP)
- Total bilirubin (TBIL)
- International normalized ratio (INR)
- Prothrombin time (PT)
- Partial thromboplastin time (PTT)

CKD stages at baseline will be summarized with counts and percentages.

The total NS at baseline will be summarized with descriptive statistics, and also according to the categories of low, moderate and high complexity (as defined in Section 6.3). The individual R, E, N, A and L components of the NS will be summarized with counts and percentages. NS at baseline will also be summarized separately for patients with a history of hypertension, for patients with a history of diabetes, and for patients with a history of both hypertension and diabetes.

The following lesion characteristics will be summarized in a per-lesion summary (i.e., over the total number of lesions recorded in the study for descriptive statistics, and as a percentage of the total number of lesions for categorical data):

- Lesion size, by greatest trans-axial diameter, will be summarized with descriptive statistics and also as categories of ≤ 4 cm and > 4 cm
- Lesion volume will be summarized with descriptive statistics
- Duration (months) between date of baseline imaging and date of cryoprocedure will be summarized with descriptive statistics
- The type of imaging used (CT, MRI, ultrasound)
- Lesion location
- Lesion classification
- Lesion shape
- Cystic or solid lesion
- Hounsfield units, separately for each of following phases
 - Non-contrast
 - Arterial Phase
 - Venous Phase
 - Delayed Phase

- Area suspicious for lesion recurrence according to Hounsfield units (as defined in Section 6.3)
- The following biopsy related data will be summarized for all patients and separately by each site
 - Biopsy performed?
 - Duration (months) between date of biopsy sample and date of cryoprocedure will be summarized with descriptive statistics
 - Type of biopsy
 - If a core biopsy was performed, number of cores taken
 - Frozen section pathology result
 - Frozen section pathology classification
 - Permanent section pathology result
 - Permanent section pathology classification
 - Fuhrman classification grade

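### The baseline profile of lesions that disappeared has no at-risk denominator, so it cannot show whether size, cystic or solid type, or pathology is related to disappearance

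*SAP*

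**What the plan says.** SAP 8.6.9.1 has two parts.

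The first summarizes lesion status at each follow-up visit, per lesion, with Wilson 95% intervals. It repeats this for patients with fewer than three freeze and thaw cycles, by procedure method, by both together, and by needle type ("By needle type (Needles with the cautery feature" against other needles). It is not split by cystic or solid type, size or pathology.

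The second part is restricted by outcome. It opens with "The following baseline results will be provided for lesions with a status of" and then names the status of a vanished lesion, recorded at one or more visits after treatment. For these lesions it asks for:

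- the cystic or solid split, worded as "Number and percentage of lesions that are cystic or solid at baseline";
- the greatest diameter before treatment, both as a continuous measure and in two groups divided at 4 cm;
- the frozen section results, and "Number and percentage in each permanent section pathology result category at baseline".

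It names no comparison group, denominator or interval.

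SAP 8.4 summarizes the same baseline features over all lesions recorded, "as a percentage of the total number of lesions for categorical data", without crossing them with disappearance. On case mix, Protocol 6.4 says only that "The typical renal lesion suitable for cryoablation is ≤ 4 cm"; it gives no distribution of sizes.

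**The concern.** Selecting lesions on the outcome and then describing their features gives P(feature | disappeared). A reader who wants to know which lesions tend to disappear needs P(disappeared | feature). The two can order the categories differently, because the first also carries how common each feature was at the start.

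No other planned analysis supplies the second quantity. SAP 8.6.4 splits by baseline size, but for recurrence and progression with enhancement. The Cox models in SAP 7.2 include size and histological type, but for time-to-event endpoints. SAP 8.8.1 describes lesions after treatment without crossing baseline features with status. This list is therefore the only planned output that links these features to complete disappearance, and a reader is likely to use it for that purpose. If most treated lesions are ≤4 cm, most vanished lesions may be ≤4 cm even when larger lesions disappear at the same or a higher rate.

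A smaller issue is that the list is on an 'ever' basis. A lesion later recorded as recurrent or present again stays in it, and a lesion imaged more often has more chances to enter it.

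**Working it through.** The documents give no figure to reproduce. The check compares what the table would show with the underlying rates.

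**Inputs, all assumed.** s is the baseline share of the more common type; the documents do not give it, so 60% to 95% is shown. rM and rm are the disappearance rates in the more and less common types. They are set first at 20% and 20%, then at 20% and 40%.

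**Formula.** Share of the more common type among vanished lesions = s·rM / [s·rM + (1−s)·rm]. It falls below one half only if rm/rM exceeds s/(1−s).

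| s | Share shown, 20% and 20% | Share shown, 20% and 40% | Rate ratio above which the less common type leads |
|---|---|---|---|
| 60% | 60% | 0.12/0.28 = 42.9% | 1.5 |
| 70% | 70% | 0.14/0.26 = 53.8% | 2.3 |
| 80% | 80% | 0.16/0.24 = 66.7% | 4.0 |
| 85% | 85% | 0.17/0.23 = 73.9% | 5.7 |
| 90% | 90% | 0.18/0.22 = 81.8% | 9.0 |
| 95% | 95% | 0.19/0.21 = 90.5% | 19 |

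With equal rates the table returns the case mix exactly. With unequal rates it returns the case mix shifted by the rate ratio. At a 60% share and a twofold ratio, the less common type leads, which is the right direction. From 70% upward it does not.

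**Illustration with counts.** SAP 4.4 says "Approximately 250 patients are expected to participate in TRACE". Assume one lesion each, so 250 lesions, with s = 80%: 200 of the more common type and 50 of the other.

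- Vanished: 200 × 0.20 = 40 and 50 × 0.40 = 20.
- Planned table: 40/60 = 66.7% against 20/60 = 33.3%.
- Row rates: 40/200 = 20.0% (Wilson 95% interval 15.0% to 26.1%) against 20/50 = 40.0% (27.6% to 53.8%).

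The same data give opposite orderings.

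**Comparison with SAP 8.4.** If the 8.4 distribution described the same lesions, the direction could be recovered. At s = 85% and a twofold ratio, 73.9% among vanished lesions against 85% at baseline correctly shows the more common type under-represented. The denominators do not match, however. SAP 8.4 counts all recorded lesions, while SAP 8.7.1 separately counts lesions found at baseline but not treated, and Protocol 8.2 expects the extent of follow-up data to vary between subjects. A lesion with no follow-up status cannot be recorded as gone. The documents do not allow the size of this mismatch to be computed.

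**The case against.** The strongest reply is that the list only describes a subgroup. It sits under additional efficacy assessments, lesion status is not among the efficacy endpoints listed in SAP 6.4, no test or comparison is attached to it, and SAP 4.4 says the study has no power for formal analysis. Profiling a subgroup by number and percentage is ordinary practice and correct for what it states. The baseline distribution is available in SAP 8.4 for anyone who sets the two tables side by side, and size is examined with a proper denominator for recurrence and progression in SAP 8.6.4.

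Most of this stands, and it limits the point to interpretation. It does not remove the point: the comparison with 8.4 is not planned and uses a wider set of lesions, and neither 8.6.4 nor the Cox models address disappearance.

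A reader might infer more than the documents support:

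- That the table simply reproduces the case mix. This is exact only when the rates are equal.
- That it will point the wrong way, or that readers will conclude small lesions respond better. Both depend on a case mix and rates the documents do not give, and at a 60% share with a twofold ratio the direction is right.
- That the SAP fixes the denominator as the vanished lesions. It does not say so, and the table shells are a separate document. It is an inference from the restriction placed on the whole list.
- That lesions are known to reappear after being recorded as gone. Nothing in the documents shows this, and status is also reported visit by visit.

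**Conclusion.** The point holds as a limit on interpretation. Read alone, the planned percentages cannot show whether a baseline feature is related to disappearance, and they could suggest the opposite of the true ordering. With a twofold higher rate in the less common type, that happens across assumed baseline shares of 70% to 95% (54% to 90% of vanished lesions) and not at 60% (43%). The conclusion rests on the natural reading of the denominator and on assumed shares and rates. No listed endpoint, test or primary conclusion is affected. The change is worth making because it is cheap and uses the within-group percentages and intervals that the same section already applies to other splits.

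**What to change.** Keep the table as a descriptive additional assessment and extend it:

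- For each baseline category, give the number of treated lesions with at least one recorded follow-up status, the number ever recorded as 'No longer present', and the row percentage with a Wilson 95% interval.
- Show baseline diameter side by side for lesions that did and did not disappear.
- Flag lesions later recorded as recurrent or present again.
- Show pathology rows only for lesions with their own biopsy result, and state the number missing. SAP 8.4 warns that, where several lesions were treated, individual results may not exist.

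The cost is one larger table shell, built from fields the SAP already summarizes. An 'ever' summary is proposed because rates by visit for every pathology category would leave very sparse cells. Even so, rare categories will have small cells and wide intervals, and an 'ever' percentage still depends on how often each lesion was imaged.

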8.6.10 Assessment of Poolability

Since this is a multi-center study, analysis will be performed by pooling data across study sites. It is expected that data will be poolable across study sites since all sites and investigators will follow a common protocol with identical inclusion/exclusion criteria (same population), treatment, and outcome assessment. Therefore a statistical assessment of poolability is not planned.

8.7 Analysis of Safety

Safety analyses will be performed on both the ITT and RCC populations. The procedural and intra-operative data will be given for both the ITT and RCC populations.

8.7.1 Procedural and intra-operative data

The following procedural and intra-operative data will be summarized using descriptive statistics, or as a number and percentage for categorical data.

The following data will be summarized in a per-patient analysis:

- Procedure method (open, laparoscopic, percutaneous); this data will also be summarized by site, and also by NS complexity categories at baseline
- Surgical approach type (not applicable, transperitoneal, retroperitoneal, hand-assisted, single port, natural orifice transluminal endoscopic surgery [NOTES], other)
- Type of Galil Medical cryoablation system used (SeedNet, Presice, Visual-Ice)
- Method of monitoring used to place cryoablation needles (CT, MRI, ultrasound)
- Method of monitoring iceball formation (CT, MRI, ultrasound)
- Completion of cryotherapy (yes, no)
- Achievement of technical success at first post-cryoablation imaging assessment (yes, no)
- Who performed the procedure? (interventional radiologist [IR], urologist, IR and urologist together, other); this data will also be summarized by site
- Type of anesthesia used (general, regional, local only, conscious); this data will also be summarized by site
- Total anesthesia time (in minutes)
- Estimated blood loss during procedure (in cc)
- Total duration of operation (in minutes); this data will also be summarized by NS complexity categories at baseline
- Type of hemostatic agents or maneuvers used (none, compression, suturing, Floseal, Gelfoam, Surgicel, other)
- Number of lesions identified at baseline but not treated with cryoablation (categorical)
 - Note: the data should only be taken from the first (date) Follow-up Lesion Assessment for each subject
- Number of lesions treated with cryoablation (categorical)
- Number of freeze and thaw cycles; this data will also be summarized by NS complexity categories at baseline
- Involvement of the kidney's collecting system, according to the following fields on the eCRF:
 - Did the iceball appear to touch the collection system? (yes, no)
 - Did the iceball appear to involve (engulf) the collection system? (yes, no)
 - Was there evidence for new gross hematuria during the course of the procedure potentially due to involvement of the iceball with the collecting system? (yes, no)
- Post-operative hematocrit (in %)

- Time from initial diagnosis of the suspicious renal mass to the date of cryoprocedure (in months)
- Length of hospital stay (in hours)
- Surgical procedures performed during the patient's hospital stay? (yes, no)
- Extended hospital stay needed due to an adjunct procedure? (yes, no)
- Conversion to another surgical approach? (yes, no)
- Narcotics required post-op? (yes, no)

The following data will be summarized in a per-lesion analysis:

- Lesion in right or left kidney (right, left)
- Was embolization performed prior to cryoblution? (yes, no)
- Number and type of cryosurgery needles used; this data will also be summarized by NS complexity categories at baseline
- Hilar clamping performed? (yes, no)
- Use of thermal sensors (yes, no)
- Additional ablation cycles required on lesion? (yes, no)

The following data will be summarized in a per-cycle analysis:

- Freeze time (in minutes) within a cycle
- Thaw times (in minutes) within a cycle
- Lowest temperature achieved at end of each freeze cycle, separately for temperature at the center and at the periphery
- Method of thaw (active, passive)

The following will also be summarized in a per-lesion analysis:

- Total freeze times (in minutes) over all cycles
- Total thaw times (in minutes) over all cycles
- Lowest temperature achieved at end of all freeze cycle, separately for temperature at the center and at the periphery

8.7.2 Adverse Events

The number and percentage of patients with the following complications will be given, together with 95% CIs for the percentages, computed using the method of Wilson (1927):

- Intra-operative device complication
- Intra-operative device complication related to the malfunction of the cryoablation system cryosurgery
- Intra-operative patient complication

AEs will be summarized by the code list provided in the eCRF in descending order of frequency; a patient will only be counted once per code. Patient counts and percentages (and 95% CIs) and event counts will be presented for the following summaries.

- Overall summary of AEs, including
 - total number of AEs, SAEs, UADEs
 - total number of AEs, SAEs, UADEs by the following subgroups:
 - CTCAE grade
 - Clavien classification
 - Site
 - Procedure method
 - NS complexity category at baseline (as defined in Section 6.3)
 - ASA score
 - Baseline lesion classification (i.e., exophytic, mesophytic, endophytic); AEs for patients with multiple lesions with different classifications will be in a separate category.
 - Did iceball appear to touch the collection system?
 - Comorbidities (HIV/immunocompromised; diabetes; hypertension; obesity; blood clotting disorder; abdominal surgery; cardiovascular; retroperitoneal surgery; von Hippel-Lindau; cancer, other than renal)
- All AEs
- All AEs by CTCAE grade
- All AEs by baseline lesion classification (i.e., exophytic, mesophytic, endophytic); AEs for patients with multiple lesions with different classifications will be in a separate category
- All AEs by the comorbidities listed above
- All SAEs
- All UADEs
- All AEs with CTCAE grade ≥ 3
- All fatal AEs (CTCAE grade 5).

8.8 Other Analyses

8.8.1 Post-treatment lesion characteristics

The analyses described in this section will be performed on the ITT and RCC populations.

The following lesion characteristics will be summarized in a per-patient summary, separately for each post treatment visit:

- Duration (months) between date of cryoprocedure and date of imaging will be summarized with descriptive statistics
- The type of imaging used (CT, MRI, ultrasound)
- Number of new lesions identified which were not present at baseline
 - Number of new lesions that are ipsilateral
 - Number of new lesions that are contralateral

The following lesion characteristics will be summarized in a per-lesion summary, separately for each post treatment visit (i.e., over the total number of lesions recorded in the study for descriptive statistics, and as a percentage of the total number of lesions for categorical data):

- Lesion in right or left kidney (right, left)
- Lesion size, by greatest trans-axial diameter, will be summarized with descriptive statistics and also as categories of ≤ 4 cm and > 4 cm
- Lesion volume will be summarized with descriptive statistics
- The type of imaging used (CT, MRI, ultrasound)
- Lesion location
- Lesion classification
- Lesion shape
- Cystic or solid lesion
- Hounsfield units, separately for each of following phases
 - Non-contrast
 - Arterial Phase
 - Venous Phase
 - Delayed Phase
- Area suspicious for lesion recurrence according to Hounsfield units (as defined in Section 6.4.1)
- Biopsy performed?
- Duration (months) between date of cryoprocedure and date of biopsy sample will be summarized with descriptive statistics
- Type of biopsy
- If a core biopsy was performed, number of cores taken
- Frozen section pathology result
- Frozen section pathology classification
- Permanent section pathology result
- Permanent section pathology classification
- Fuhrman classification grade

8.8.2 New therapies for renal cancer

The analyses described in this section will be performed on the ITT and RCC populations, separately for each visit.

The following will be summarized by the number and percentage of patients:

- Disease free status
- Patients who received a new therapy for renal cancer
- Patients who received local and systemic therapy

- Patients who received subsequent cryoablation (note: these patients will need to be identified manually from the response to the ‘Specify type of local or systemic therapy’ field on the ‘Follow-up/Further cancer therapy’ eCRF page)

Duration (months) between date of cryoprocedure and date of new local therapy will be summarized with descriptive statistics. Also, the duration (months) between dates of first and subsequent cryooperations (retreatments) will be summarized.

8.8.3 Comparison of investigator and non-investigator imaging results

The analyses described in this section will be performed on the ITT population.

The agreement between investigator and non-investigator assessed lesion sizes will be assessed using Bland-Altman analysis (Bland, 1986) of the per-patient analysis lesion measurements (described in Section 6.4.1). This will include calculation of the 95% limits of agreement. This analysis will be performed for the largest lesion measurement (i.e., largest of AP, TR, CC, and greatest trans-axial diameter), separately for each visit (including baseline).

Agreement in the lesion classification (exophytic, meophytic or endophytic), will be assessed using Cohen's kappa coefficient (Cohen, 1960), and interpreted according to Landis and Koch (1977).

8.8.4 Renal function status

The analyses described in this section will be performed on the ITT and RCC populations.

The change from baseline in eGFR and sCR will be summarized using descriptive statistics for each follow-up visit. The change from baseline in CKD stage will be summarized in a shift table.

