6.3. Exclusion Criteria

Patients who meet the following exclusion criteria are not eligible for enrollment in the registry:

1. Patient is either currently using or has used within the last 30 days an investigational product of any type.
2. Patient has metastatic disease to or from the kidney.

3. Patient has had previous therapy on the index lesion (e.g. radiofrequency, cryoablation, partial nephrectomy).

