6.6 Other Variables

6.6.3 Renal function

6.6.3.1 Estimated Glomerular Filtration Rate

The estimated Glomerular Filtration Rate (eGFR) will be calculated within the eCRF using the Modification of Diet in Renal Disease (MDRD) formula. For serum creatinine (sCR) in mg/dL, and age in years:

$$\text{eGFR} = 175 \times \text{sCR}^{-1.154} \times \text{Age}^{-0.203} \times [1.212 \text{ if Black}] \times [0.742 \text{ if Female}].$$

The change from baseline in eGFR will be computed.

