6.6.3.2 Chronic Kidney Disease stages

Chronic kidney disease (CKD) stages will be computed from the eGFR values as follows:

- Stage 1: eGFR ≥ 90 mL/min
- Stage 2: eGFR ≥ 60 and < 90 mL/min
- Stage 3A: eGFR ≥ 45 and < 60 mL/min
- Stage 3B: eGFR ≥ 30 and < 45 mL/min
- Stage 4: eGFR ≥ 15 and < 30 mL/min
- Stage 5: eGFR < 15 mL/min

The change from baseline in CKD stages will be computed.

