8.3 Analysis Populations

8.3.1 Intent To Treat (ITT) Population

All patients where a cryoprocedure was attempted with a Galil Medical Cryoablation System and needles and who met the study eligibility criteria will form the Intent-to-Treat (ITT) population. This population will be used for the analysis of all efficacy and safety data. Patients in the ITT population will be identified as follows:

- 1) First include all patients with a date of cryotherapy recorded
- 2) Then exclude any patients who have been manually identified as having not met all eligibility criteria from a review of monitoring reports.

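### SAP 8.8.4 has no rule for patients on dialysis at baseline, whose creatinine and eGFR changes do not measure kidney function

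*SAP*

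**What the plan says.** Protocol 6.3 opens with "Patients who meet the following exclusion criteria are not eligible for enrollment in the registry" and lists three criteria: recent use of an investigational product, metastatic disease, and earlier therapy on the index lesion. None concerns renal function, and neither do the inclusion criteria in 6.2. SAP 8.4 lists dialysis status among the disease-related baseline characteristics to be tabulated, so the field exists.

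The protocol names renal function, as eGFR, among its outcomes (Synopsis, 8.4, 8.5). SAP 6.6.3.1 says that eGFR "will be calculated within the eCRF using the Modification of Diet in Renal Disease (MDRD) formula", that is, from serum creatinine, age, race and sex. SAP 6.6.3.2 adds "Chronic kidney disease (CKD) stages will be computed from the eGFR values as follows"; the lowest category is stage 5, below 15 mL/min, and there is no dialysis category.

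SAP 8.8.4 sets the analysis: "The change from baseline in eGFR and sCR will be summarized using descriptive statistics for each follow-up visit", and "The change from baseline in CKD stage will be summarized in a shift table". On the population it says "The analyses described in this section will be performed on the ITT and RCC populations". The ITT definition in SAP 8.3.1 carries no dialysis condition. No exclusion, stratum or sensitivity summary for dialysis appears in 6.6.3 or 8.8.4.

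**The concern.** The renal-function summaries are meant to show what happens to the kidney after cryoablation. Dialysis removes creatinine from the blood. In a dialysed patient, the measured value therefore depends on the dialysis, and so does an eGFR calculated from it. A change between two visits tells the reader neither about native kidney function nor about harm from the ablation.

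The plan collects the field that identifies these patients but does not use it where it matters. A few such patients have large creatinine values and can have large absolute changes, so they could dominate the spread of the sCR change and possibly move its mean. In the shift table they could appear as stable, worse or better for reasons that have nothing to do with the treatment.

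**Working it through.** The plan states no figure to reproduce. The check applies the SAP's own formula and cut-offs, then a simple mixture.

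**Inputs from the documents.** eGFR = 175 × sCR^-1.154 × Age^-0.203 × [1.212 if Black] × [0.742 if female] (SAP 6.6.3.1). Stage 4 is 15 to below 30, stage 5 is below 15 (SAP 6.6.3.2). About 250 patients (SAP 4.4).

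**Assumptions (not in the documents).** Non-dialysis patients: mean sCR change +0.10 mg/dL, SD 0.3; mean eGFR change -5 mL/min. Dialysis patients: share p of 1% to 5%; sCR change D of -3 or +3 mg/dL, SD 1.5; eGFR change between -5 and +5 mL/min.

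**1. CKD stage.** Setting eGFR = 15 and solving for creatinine gives the level above which a patient is in stage 5. For a non-Black man aged 68: (175 × 68^-0.203 / 15)^(1/1.154) = 4.00 mg/dL; for a non-Black woman aged 68, 3.09. Across ages 45 to 80, both sexes and both race terms, the range is about 3.0 to 5.1. For the man aged 68:

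- sCR 6 to 8 gives eGFR 9.4 to 6.7: stage 5 at both times. No rise in creatinine can register as worsening.
- sCR 3.5 to 5 gives eGFR 17.5 to 11.6: stage 4 to 5, which reads as worsening. The reverse reads as improvement.

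So there is a floor for those who start in stage 5 and misclassification for those who start above it.

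**2. Mean and SD of sCR change.** Pooled mean m = (1 - p) × 0.10 + p × D. Pooled variance = (1 - p) × [0.3² + (0.10 - m)²] + p × [1.5² + (D - m)²].

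| Share p | Mean, D = -3 | SD | Mean, D = +3 | SD |
|---|---|---|---|---|
| 1% | 0.07 | 0.45 | 0.13 | 0.44 |
| 2% (5 of 250) | 0.04 | 0.57 | 0.16 | 0.55 |
| 3% | 0.01 | 0.66 | 0.19 | 0.63 |
| 5% | -0.06 | 0.81 | 0.25 | 0.77 |

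Example at 2%, D = -3: m = 0.98 × 0.10 - 0.02 × 3 = 0.038; variance = 0.98 × (0.09 + 0.0038) + 0.02 × (2.25 + 9.229) = 0.322; SD = 0.57.

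**3. Changes in both directions.** At 2%, with half at -3 and half at +3, the dialysis group has mean 0 and variance 1.5² + 3² = 11.25. Then m = 0.98 × 0.10 = 0.098, and variance = 0.98 × 0.09 + 0.02 × (11.25 + 0.098²) = 0.313, so SD = 0.56. The mean is almost unchanged, but the SD still nearly doubles.

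**4. Mean eGFR change.** At 5% with the extreme of +5: 0.95 × (-5) + 0.05 × 5 = -4.5, a shift of 0.5 mL/min. At 2%: 0.98 × (-5) + 0.02 × 5 = -4.8, a shift of 0.2.

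**5. Median.** If all dialysis patients lay beyond one end of the other patients' distribution, the pooled median would fall at the other patients' 0.48/0.98 = 49.0th or 0.50/0.98 = 51.0th percentile at a 2% share, and at the 47.4th or 52.6th at 5%. It is largely protected.

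**The case against.** The strongest reply is that the effect may be nil. The documents do not say how many patients are on dialysis; a field to be tabulated can come out as zero. Laboratory values are collected only as available (Protocol 7.1 and 7.5), so a dialysis patient may lack one of the two values. This stands, and the point is conditional on at least one such patient having paired values.

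Second, a reader might infer that the shift table can never show a dialysis patient worsening. That is true only of those in stage 5 at baseline, because stage is computed from eGFR alone. A reader might also infer that a percentage worsening in CKD stage is understated. The SAP plans no such pooled percentage; a shift table sets baseline stage against later stage, so patients starting in stage 5 can be seen as such.

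Third, the protocol's own renal outcome is eGFR, and its mean barely moves. Serum creatinine change is a SAP addition. The shift in mean sCR also needs changes that run mostly one way. If each of five patients were equally likely to move by +3 or -3, all five would agree in direction with probability 2 × (1/2)^5 = 1/16, about 6%. These points stand and limit the size of the problem.

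Fourth, SAP 7.1 plans median, interquartile range, minimum and maximum, as well as full listings, and 8.8.4 contains no test. So no error rate is affected, and an attentive reader could notice outliers. This does not answer the point about the reported SD or the stage shifts: nothing in 8.8.4 separates dialysis patients from the rest.

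**Conclusion.** The omission is real. Followed as written, SAP 8.8.4 mixes values that do not measure kidney function into the renal-function summaries whenever dialysis patients have paired creatinine. That they may be enrolled follows from the absence of any exclusion, not from an explicit statement.

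The main effect is on the SD of sCR change, which nearly doubles under the assumed 2% share whichever way the changes run. The mean of sCR change may shift if they run mostly in one direction. The effect on mean eGFR change is small, and the median and interquartile range are largely protected. The CKD shift table has a floor for stage 5 starters and spurious shifts for those with lower creatinine. All shares and changes are assumptions.

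The documents do not support saying that the reported mean will be distorted, or that the protocol's eGFR outcome is seriously compromised. This is a modest defect of interpretation in a named outcome. It is worth correcting because the correction is cheap.

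**What to change.** In SAP 8.8.4:

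- report the number of patients on dialysis at baseline, for the ITT and RCC populations;
- exclude them from the summaries of change in sCR and change in eGFR;
- show them as a separate dialysis category in the CKD shift table, rather than by eGFR-derived stage.

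Leave the Cox covariate analysis in 7.2 unchanged. Setting baseline eGFR to missing for these patients would drop them from any complete-case model that uses it, which is a larger change than this point justifies. Eligibility and all other analyses also stay as they are.

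The cost is a few sentences, a filter on a field already planned for tabulation, and a slightly smaller n in these tables. The change covers dialysis at baseline only: the event schedule and SAP 8.8 name no follow-up dialysis item from which a later start could be identified.
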